Data collection and storage protocols will minimize the use of identifying information. All EHR data will be de-identified by the Grant Reporting Manager before being shared with the study team for analysis. All research participants will be identified on all research forms and logs (other than the study ID linkage forms) by unique but non-identifying codes. Code linkage files relating ID codes to names will be maintained on RedCap, a password-protected site, accessed only by the lead study staff ([name], [name], and [name]). Zoom and telephone interviews will be recorded only using CUIMC-hosted Zoom accounts, with a password required for entry into the room. Recordings of the interviews will only be recorded onto encrypted, password-protected endpoint computer temporarily. This electronic data will be maintained on the encrypted, password-protected computer files on encrypted devices with limited access to data by staff – different levels of access will depend on the person's specific level on the staff, and server security safeguards that in the aggregate provide a high degree of protection from unauthorized users. Interviews will be transcribed as quickly as possible; once transcribed and checked for accuracy, the recordings will be deleted.

All qualitative and quantitative information will be coded by identification number, so that no full names or other personally identifying information (PII) are associated with any of the data. Identity of participants – including deductive disclosure -- will not be revealed in the presentation or publication of any results from the project. All personnel working on the project will be regularly trained and re-trained about the importance of strictly respecting participants' rights to confidentiality and specific approaches to ensure such protections. The only data for which PII cannot be inextricably separated from the data is a voice print. Special steps will be taken to protect this data.

Confidentiality and privacy for audio/video recording of human subjects

The project will ensure the following steps are followed, and will include these steps in the consent forms for participants:

1. Participants will be informed that the interviews will be recorded. Their voices will be recorded, but no other likenesses will be recorded. Names and likenesses (pictures or live video) will not be recorded. The interviewer will instruct participants to change their screen name on Zoom to their study ID.
2. The recording will not start until the participant has turned off their video camera and changed their screen name to their study ID.
3. The video recording will be recorded and viewed by the Research Coordinator and the Principal Investigators. The recording will be downloaded to extract the transcription of the audio feed. No identifiers will be included in the transcriptions. The Research Coordinator will review the transcript for accuracy, consulting the original audio as needed. As soon as the accuracy of the transcription is confirmed, the recordings will be destroyed from all locations.
4. The video recordings (before destruction) and the transcriptions (without identifiers) will be stored temporarily on an encrypted and password protected computer.
5. There will be no future use of the recordings, once the recordings are transcribed.

Participants will be consented prior to the start of the interview, and all of these points will be reviewed.

9. Privacy Protections

We will ensure confidentiality is protected by taking several steps. Per CUIMC Institutional Review Board (IRB) guidelines, all members of the study staff must complete trainings in human subjects protection and HIPAA requirements, as well as ongoing training by the PIs in all aspects of human subjects protection. The platforms we will use for data collection, Zoom and either REDCap or Qualtrics, will use only the CUIMC-hosted versions, which are HIPAA compliant. For purposes of the research database, each participant will be assigned a unique identifier that bears no systematic relation to the family, or school, or SBHC records. Information to be excluded from the research database includes names of study participants, addresses, telephone numbers, school, clinician, and other information that has the potential to identify individuals. All outcome data will be de-identified by HIPAA standards using the "safe-harbor" method (i.e., all 18 PII elements will be stripped) prior to being stored on a password-protected, encrypted server.

10. Potential Risks

Participation in this research involves minimal risk, defined in the Federal guidelines as "the probability and magnitude of harm anticipated in the research are not greater in and of themselves than those ordinarily encountered in daily life or during the performance of routine physical or psychological examinations or tests."

- (1) It is possible that the adolescent participants will experience some inconvenience, embarrassment, or distress while participating in the interviews or completing surveys.

Survey and interview participants will be reminded of the option to not answer any questions or to stop the survey or interview at any time. Adolescent participants reporting distress to the study team will be referred to onsite mental health providers that are always available at the SBHCs. Adolescent participants have access to primary care through the SBHCs, if parental permission is on file for them to receive primary care.

Since the risks to individual study participants are minimal, the study appears to be readily justifiable.

11. Data and Safety Monitoring

This is a minimal risk study. The PIs ([name] and [name]) will be responsible for all data safety and monitoring. They will have responsibility for ensuring that the policies outlined above to minimize risk – including staff training, storing identifiers separately from survey and interview data, and storing all data on encrypted, password-protected servers – are followed. The PIs will conduct regular checks of data storage procedures, ensuring, for instance, that: any recordings have been destroyed following transcription; access to electronic data is limited to trained study staff, and the research database does not include any personally identifying information.

In their weekly team meetings, Drs. [name] and [name] will review with the study staff weekly data reports regarding all study-related activities. This will include the sample size and proportion of approached contacts, eligibility rates (and reasons), consent/refusals, and surveys and interviews completed.

All study personnel will report any study-related adverse events and/or unanticipated problems involving risks to participants to Drs. [name] and [name]. In the case of any adverse event or unanticipated problem, Drs. [name] and [name] will notify the CUIMC IRB. [name] will, if appropriate, inform the Merck Project Officer in writing of any actions taken by the IRBs as a result of such adverse events.

12. Potential Benefits

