A Prospective Observational Study of the Implementation of Telehealth-Supported LARC Provision in School-Based Health Centers

NCT04840836

IRB approval: Jan 5, 2024

1. Study Purpose and Rationale

Study Purpose

In this proposed prospective observational study, we will describe in detail the implementation of a **hybrid model of telehealth-supported long-acting reversible contraception (LARC) service provision in a network of 6 school-based health centers (SBHCs)** in New York City that serve adolescents and young adult high school students age 13-22 years (hereafter referred to as “adolescents”). We will use quantitative and qualitative data, leveraging surveys combined with electronic health record data, to assess satisfaction with telehealth-supported LARC care, and uptake and continuation of LARC methods following introduction of telehealth-supported LARC service delivery in SBHCs. The findings from this study, given the SBHC setting, have the potential to inform and improve LARC service delivery for adolescents far beyond New York City and the SBHC setting.

Specific Aims:

Aim 1. Quantify uptake of LARC (contraceptive implant, IUD) within the SBHC network following implementation of telehealth-supported LARC provision.

Aim 1.1 Among all patients who had a telehealth visit for contraceptive counseling, quantify the number and rate of telehealth LARC consultations and LARC initiations overall, and compare by LARC type (contraceptive implant vs. IUD).

Aim 1.2 Subgroup analyses of LARC initiation (overall and by type) by patient characteristics (e.g. age group, race/ethnicity, sexual activity in last 90 days).

Aim 2: Describe the implementation of telehealth-supported long-acting reversible contraception (LARC) service provision in school-based health centers (SBHCs) using mixed methods.

Aim 2.1 Assess, through quantitative surveys among LARC initiators, patients’ experience and satisfaction with telehealth-supported care.

Aim 2.2 Explore, through qualitative surveys with a purposive-sampled subset of LARC initiators, adolescents’ experience with the telehealth-supported care and perceived benefits and drawbacks of telehealth care overall and for supporting LARC services (Ambresin et al., 2013).

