This two-year study will have three phases: 1) a 4-month study initiation phase; 2) a 12-month enrollment and surveying phase; 3) and a 6-month follow-up observation phase. Continuation analyses will rely on person-time, so that study participants will contribute a minimum of 6 to a maximum of 19 months observation time, depending on their time of enrollment.

Statistical Procedures. [name] will have lead responsibility for conducting statistical analyses, supervising data cleaning, and logic checks conducted by the Research Coordinator, and working with the Biostatistician on model building. As this is a prospective observational study that seeks to enroll all patients who receive telehealth-supported LARC services over a 12-month period, the sample size will be determined by patient flow and participation rates.

Aim 1 (Secondary Outcome): Quantify uptake of LARC (contraceptive implant, IUD) within the SBHC network following implementation of telehealth-supported LARC provision

Aim 1.1 Making use of a newly-implemented electronic health record (EHR) system, Epic, we will assess uptake of contraception, quantifying the number and proportion of contraceptive method initiation (uptake), assessing each month:

- 1) absolute number of contraceptive counseling visits via telehealth;
- 2) absolute number of LARC telehealth consultations (a LARC consultation being defined as a visit in which an insertion is scheduled);
- 3) absolute number of LARC initiations by type (contraceptive implant, IUD);
- 4) LARC initiation visits as a proportion of contraceptive counseling visits (overall, and by LARC type [contraceptive implant, IUD]);

¹ The current SBHA Census does not provide data on how many SBHCs dispense contraception; the most recent data on this are from the 2007-08 census and are not presented here.

- 5) LARC initiation visits as a proportion of all contraceptive method initiation visits (overall, and by LARC type);
- 6) LARC initiation visits as a proportion of LARC telehealth consultations (defined as a visit in which a LARC initiation was scheduled; overall and by LARC type);

and 7) relative share of initiations of contraceptive implant and IUD, among LARC initiators.

Statistical Methods (Aim 1.1)

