- 1) Descriptive analyses (frequency tables) will present, by month, the absolute numbers of contraceptive counseling visits, LARC consultations (with a scheduled insertion) (overall, and by LARC type [contraceptive implant, IUD]); and initiations (overall, and by LARC type [items 1-3 above]).
- 2) Descriptive analyses will present the proportion of LARC initiations out of the number of contraceptive counseling visits [item 4], contraceptive initiations for all methods [item 5], and telehealth-based LARC consultations [item 6]. A consultation is defined as a visit for which a LARC initiation was

scheduled. These analyses will be presented in frequency tables.

3) For each of the uptake outcomes listed above [items 4-7], bivariate statistical analyses will compare the outcome proportions for contraceptive implant vs. IUD, using Chi-square tests.

Aim 1.2 Bivariate analyses will assess the uptake of LARC methods (overall, and contraceptive implant vs. IUD) by patient subgroup, examining LARC initiation (in absolute numbers, and as a proportion of telehealth consultations) by patient characteristics (age, race/ethnicity, gender identity, sexual orientation, sexual activity in last 90 days, gravidity, parity).

Statistical Methods (Aim 1.2)

Bivariate Chi-square tests will compare the proportion who initiated out of those who had 1) a telehealth contraceptive counseling consultation and 2) a LARC consultation for which an insertion was scheduled across subgroups defined by age group (using age categories consistent with the CDC's Youth Behavior Risk Surveillance System, ages 13-14, 15-17, 18-19, 20 and older); race/ethnicity (Hispanic + Black, Black non-Hispanic, Hispanic of any other race, non-Hispanic race other than Black); gender identity (female, male, transmale, gender non-conforming); sexual orientation (straight/heterosexual, gay/lesbian, bisexual, asexual); sexual activity (any/no sexual activity in last 90 days); gravidity (any/no pregnancy history); parity (any/no live birth).

Aim 2: Describe the implementation of telehealth-supported long-acting reversible contraception (LARC) service provision in school-based health centers (SBHCs) using mixed methods.

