Aim 2.1 For all patients who initiate a LARC method over the 12 month enrollment period (estimated n=102), we will conduct online follow-up quantitative surveys with all adolescent patients who completed their in-person visit to initiate LARC method (contraceptive implant, IUD) to assess their experience with telehealth-supported care, including: when, where, and using what device they participated in the telehealth video session (e.g. laptop, smartphone, or tablet; with or without headphones); satisfaction with telehealth session (comfort in using telehealth, perceived privacy, extent to which questions were answered); how prepared they felt for the insertion visit; self-efficacy to manage side effects; time (in days) from telehealth visit to method initiation visit; whether attended scheduled follow-up telehealth visit (yes/no); and time (in days) between initiation and follow-up telehealth visit. These surveys will also collect data on interaction with health educators and/or peer health educators. We conservatively estimate a survey sample size of 87 for these surveys (85% participation).

Statistical Methods (Aim 2.1)

Descriptive analyses (frequency tables, means with standard deviations) will describe the telehealth experiences for all survey respondents. Bivariate statistical analyses will compare experiences between contraceptive implant and IUD initiators. We will use Chi-square for dichotomous outcomes, t-tests for means, and Wilcoxon Mann Whitney tests for medians (e.g. time in days between visits).

Aim 2.2 Qualitative interviews with 30 patients, using purposive sampling to ensure a range of perspectives (e.g. age, LARC method, health educator engagement). These qualitative surveys will expand on the aspects covered in the quantitative surveys and will explore, in greater detail, adolescents' experience with the telehealth-supported care from the SBHC, including prior experience with telehealth, perceived benefits and drawbacks of telehealth care overall and for supporting LARC services, specific domains of questions or concerns about side effects and maintenance of their LARC method, and dimensions of youth-friendly care (Ambresin et al., 2013).

Statistical Methods (Aim 2.2)

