With a sample size of 102 and the margin of non-inferiority of 10 percentage points, the proposed study has 80% power to declare the non-inferiority of the telehealth-supported LARC services in a network of SBHCs in a one sample, one-sided Z test. This power analysis is for the primary efficacy outcome of interest, i.e., LARC continuation rate at 12 months. The reference LARC continuation rate at 12 months of 0.853 was obtained from the meta analysis conducted by Usinger, Gola, Weis & Smaldone in 2016. The studies included in their meta-analysis collected sample in the US with participants in those studies being young women aged 25 years and younger using a range of contraceptive methods. Therefore, if the true LARC continuation rate at 12 months is 0.753 or higher, the study is adequately powered to establish the non-inferiority of telehealth-supported approach. In the CHOICE Project, 12-month continuation of Copper IUDs among participants age 14-19 was 75.6% (Rosenstock et al., 2012).

Aim 3.2 (Exploratory, pending feasibility) Continuation compared to pre-Telehealth. Pending examination of the feasibility of constructing a pre-telehealth research database using the prior EHR system, compared to continuation rates within the same network prior to the implementation of telehealth-supported care, we will compare 12-month continuation (yes/no) following introduction of telehealth to 12-month continuation among LARC initiators seen the 18 month period prior to introduction of telehealth (June 2018-December 2019) *pending ability to export data from the prior electronic health record.*

3. Study Procedures

AIM 1

Participant enrollment – Aim 1: All patients who receive care at the SBHC provide informed consent for care, as well as record review for quality assurance purposes. Analyses for Aim 1 will include all female patients who have a “reproductive health visit,” which includes contraceptive counseling, contraceptive management, or contraceptive method initiation, during the study period. All patients who have a telehealth consultation with a SBHC medical provider for LARC services (conservatively estimated n=113) will be considered enrolled patients once the data are extracted from the EHR, and these will inform uptake analyses for Aim 1.

AIM 2

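### Aim 1.1 items 4 and 6 measure LARC uptake per visit although the aim is stated per patient, and no rule handles repeat visits

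*Combined protocol and SAP*

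**What the plan says.** Section 1 (Specific Aims) sets the population of Aim 1.1 as people: "Among all patients who had a telehealth visit for contraceptive counseling". Section 2, Aim 1.1, then defines the measures in visits:

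- Item 4: "LARC initiation visits as a proportion of contraceptive counseling visits".
- Item 5: "LARC initiation visits as a proportion of all contraceptive method initiation visits".
- Item 6: "LARC initiation visits as a proportion of LARC telehealth consultations", with "a LARC consultation being defined as a visit in which an insertion is scheduled".

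Statistical Methods (Aim 1.1) repeats the count of counselling visits as the item 4 denominator and applies Chi-square tests, implant against IUD, to items 4 to 7. It gives no index-visit rule, no de-duplication and no allowance for several visits by one patient.

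Statistical Methods (Aim 1.2) goes back to people: "Bivariate Chi-square tests will compare the proportion who initiated out of those who had" one of two kinds of consultation.

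The planning number 113 carries both units. Section 4 gives it as telehealth consultations, each defined as a visit. Section 2 (Power/Sample Size, Aim 3.1) and Section 3 (Aim 1) give it as patients. These agree only if each patient has exactly one consultation, which is not stated.

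**The concern.** A patient counselled three times who then receives a LARC adds one to the item 4 numerator and three to its denominator. A patient who misses an insertion and has a second telehealth visit to schedule another adds two to the item 6 denominator. The rates then reflect how often patients are seen as well as how many obtain a method.

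Repeat visits are plausible on the protocol's own account. The background in Section 1 reports that several visits may be needed to support a decision, and that in one cited study almost half of the women for whom an IUD was ordered did not come back for insertion.

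Uptake is the declared secondary outcome, and the study is meant to inform replication elsewhere. A reader of the results will want the share of patients who obtain a LARC. Aim 1.1 as defined may not give that share, and the same report could carry a different rate under Aim 1.2.

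**Working it through.** **Inputs from the plan.** 113 consultations or patients and 102 insertions (Sections 2 and 4). Past initiations: 86 implant and 43 IUD in 2018-19, 41 and 3 in 2019-20 (Section 2, Power/Sample Size). The plan states no uptake rate, power or sample size for Aim 1.1, and no number of counselled patients or of visits per patient. All repeat-visit rates below are therefore assumptions.

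**1. Implied rate.** With one consultation per patient, item 6 is 102/113 = 90.3%.

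**2. Effect of repeat scheduling visits on item 6.** With r extra scheduling visits per patient, the visit-level rate is 102 / (113 × (1 + r)).

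| r (assumed) | Calculation | Item 6 |
|---|---|---|
| 0 | 102/113 | 90.3% |
| 0.1 | 102/124.3 | 82.1% |
| 0.25 | 102/141.25 | 72.2% |
| 0.5 | 102/169.5 | 60.2% |

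Item 4 behaves in the same way: its visit-level rate is the per-patient rate divided by the mean number of counselling visits per patient. For illustration, with an assumed 300 counselled patients, 102/300 = 34.0% per patient becomes 102/450 = 22.7% at 1.5 visits each and 102/600 = 17.0% at 2.

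**3. Implant against IUD in item 6.** The 2018-19 split of 86:43 is 2:1. Applied to the plan's totals it gives about 75 implant and 38 IUD patients, with 68 and 34 initiations. Patient-level uptake is nearly equal: 68/75 = 90.7% and 34/38 = 89.5%, p = 0.84. Now let the mean number of scheduling visits per patient vary (Chi-square without continuity correction):

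| Implant | IUD | Item 6 rates | p |
|---|---|---|---|
| 1.0 | 1.1 | 68/75 = 90.7%, 34/42 = 81.0% | 0.13 |
| 1.0 | 1.25 | 68/75 = 90.7%, 34/48 = 70.8% | 0.004 |
| 1.25 | 1.25 | 68/94 = 72.3%, 34/48 = 70.8% | 0.85 |

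The split from both periods together, 127:46, gives 83 and 30 patients with 75 and 27 initiations. At 1.1 and 1.5 visits per patient the rates are 75/91 = 82% and 27/45 = 60%, Chi-square 8.07, p = 0.0045.

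A simulation of 20,000 trials used 75 and 38 patients, a true rate of 102/113 in both groups, and Poisson numbers of extra visits. The test at a nominal 5% rejected in 4.7% with no repeats, 3.6% with 0.25 extra visits in both groups, 26% with 0 against 0.1, and 74% with 0 against 0.25. The false difference comes from unequal repeat rates. Repeat visits as such do not raise the rejection rate.

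**4. Items 4 and 5.** The plan assigns no LARC type to a counselling visit, so in item 4 both types are divided by one total D. The ratio is (68/D)/(34/D) = 2.0 whatever D is, and repeat visits cannot change it. The defect is a different one: the two proportions share a denominator, so they are not the two independent samples that the Chi-square test assumes. Item 5 shares a denominator in the same way, but it contains initiation visits only and repeat counselling does not enter it.

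**The case against.** Visit-based conversion is a legitimate service measure in an implementation study. The items are tabulated monthly, and the Aim 1.2 methods would already allow a per-patient rate. The introduction to Aim 1.2 also speaks of a proportion of consultations, so the contrast between the aims is not clean. The double use of 113 suggests that about one consultation per patient is expected, and nothing says that moving an appointment makes a new consultation. All of this is fair. It shows that the distortion may turn out small. It does not supply a counting rule, and nothing commits the Aim 1.1 figures to the per-patient rate.

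Four stronger readings are tempting, and the documents do not support them.

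- A reader might infer that the post-insertion visit recorded in Aim 2.1 ("whether attended scheduled follow-up telehealth visit (yes/no") dilutes uptake throughout. An ordinary follow-up schedules no insertion, so it is outside item 6, and it is not an initiation visit, so it is outside item 5. It enters item 4 only if coded as counselling. Sections 3 and 4 list counselling, management and initiation separately and do not place it.
- A reader might extend the dilution to item 5. Only repeat initiations or method switches could distort that item.
- A reader might conclude that a false difference between implant and IUD is to be expected. It is possible in item 6 alone and needs unequal repeat rates, which the documents do not give.
- Section 3 says "Analyses for Aim 1 will include all female patients who have a" reproductive health visit. That sets the Aim 1 analysis population. It does not add another denominator for items 4 to 6.

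**Conclusion.** The point holds for items 4 and 6. Their stated unit does not match the aim or the Aim 1.2 methods, and the rates depend on visit frequency. For item 6 the loss is about 8 percentage points at 0.1 extra scheduling visits per patient (90.3% to 82.1%) and about 30 at 0.5 (90.3% to 60.2%). These sizes rest on assumed repeat rates; the direction does not. A spurious difference by type in item 6 is a conditional risk. This is more than missing detail, because the visit-level rule that the plan states would be followed as written. Aim 1 is secondary, and the primary test of 12-month continuation is unaffected.

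**What to change.** In Section 2, Aim 1.1:

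- **Item 4:** patients initiating a LARC divided by unique patients with at least one telehealth contraceptive counselling visit before any insertion.
- **Item 6:** patients initiating a LARC divided by unique patients with at least one LARC consultation, with LARC type taken from the index scheduled insertion.
- **Repeat visits:** post-insertion follow-up, rescheduling and replacement visits add to neither denominator.
- **Tests:** run the item 6 comparison of implant and IUD at patient level. For items 4 and 5, where the types share a denominator, report the proportions by type with confidence intervals in place of the two-sample Chi-square test.
- **Visit counts:** keep them in items 1 to 3 as workload measures.
- **The number 113:** say whether it counts patients or visits, and use one unit throughout.

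The cost is wording and de-duplication by patient. Section 3 (Aim 3) already plans to export all visits, so no new data are needed. One detail to confirm is that the de-identified file carries a stable patient code for counselled patients who never initiate. Section 3 (Aim 2) describes study IDs for survey contacts, while Section 9 promises a unique identifier for each participant without spelling out this group. The Grant Reporting Manager, who holds the link to the record, could assign the code before de-identification.

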Additionally, we will use Chi-squared tests to compare continuation (yes, continued/no, discontinued) between LARC types (contraceptive implant vs. IUD) at two time points: 6 months and 12 months post-initiation. Adjusted analyses using logistic regression will be conducted to compare the continuation at 6 and 12 months (yes or no) separately between contraceptive implant and IUD patients, adjusting for covariates (age, race/ethnicity, gender identity, sexual orientation, sexual activity in last 90 days, gravidity, parity). Operationalization of these covariates is outlined in Aim 1.

Power/Sample Size (Aim 3.1):

The study anticipates enrolling 113 patients, with 102 patients included in the continuation analyses for Aim 3 (primary outcome). Our sample size estimates are based on conservative SBHC clinical data from 2018-2019 and from the first seven months of 2019-20 (which was disrupted by both the transition to a new EHR Epic system and school and SBHC closures due to COVID-19); during the July 2018 to January 2020 time period, there were, respectively, 129 LARC initiations (86 contraceptive implant, 43 IUD), and 44 LARC initiations (41 implant, 3 IUD). These sample size estimates are conservative, as the SBHCs have three newly-hired and trained medical providers since the 2019-20 disrupted year.

We anticipate having complete data for the continuation analyses sample size ($n=102$). Using the new Epic EHR, at each visit within the NYP clinical network – the participating study sites in the SBHCs, as well as the emergency department, inpatient and outpatient clinics – the health care provider is required to conduct reconciliation of medications and document it in the Epic EHR. The medical providers ask every patient at every visit what their current contraceptive method is – confirming the presence of the method, and documenting in two places in the EHR (in the contraception and in medications sections). These analyses will be able to assess continuation (presence of the device at a visit) and censoring

(device removal, device removal with re-insertion).

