Adolescents and young adult high school students are the primary study participants. This study will describe in detail the implementation of a hybrid model of telehealth-supported LARC service provision in a network of 6 SBHCs in New York City that serve students who are between the ages of 13 and 22 years. The specific age range of the students was selected because it reflects the age range of students served by the 6 SBHCs. We are limiting our enrollment to high school students because the study is based in SBHCs. We have used the enrollment and retention strategies proposed in this application in our past research.

Patient population. Based on SBHC clinical data from the full academic year (2018-19), we estimate that, over the 12 month cohort there will be 113 telehealth consultations, defined as a visit in which an appointment is scheduled to initiate a LARC methods (Aim 1), and 102 LARC insertions (Aim 2). The SBHC

² This figure represents total number of visits for all patients, including patients receiving mental health care, who have regularly scheduled repeat visits. The average number of visits per year per unique female patient among LARC users is anticipated to be lower.

patient population, as a whole, is 69% Hispanic and 26% Black (not mutually exclusive), with an average age of 16 years. The majority of patients have their visits covered by Medicaid.

Participants will be eligible to participate in the study if they are: 1) an enrolled patient at the participating SBHC; 2) age 13-22 years; 3) female; 4) had a visit at the SBHC during the study period that is coded as a “reproductive health visit” including contraceptive counseling, contraceptive management, and contraceptive method initiation.

For Aims 2 and 3, individuals will be excluded if they: 1) are younger than age 13 years; 2) are older than age 22; 3) are not an enrolled patient of the participating SBHCs; 4) did not initiate a LARC method; 5) are a person without a uterus; 6) are unable to read, speak, and understand either English or Spanish.

5. Recruitment

Aim 2.1: Adolescent Survey Participants:

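### The implant-versus-IUD Chi-square in Aim 1.1 suits only item 6; items 4, 5 and 7 have no two separate groups, and a two-group test there understates the variance

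*Combined protocol and SAP*

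**What the plan says.** Section 2, Aim 1.1 (a secondary outcome) lists seven uptake measures. The four that matter here are:

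- Item 4: "LARC initiation visits as a proportion of contraceptive counseling visits (overall, and by LARC type".
- Item 5: "LARC initiation visits as a proportion of all contraceptive method initiation visits (overall, and by LARC type".
- Item 6: LARC initiations over LARC telehealth consultations, overall and by type. Statistical Methods (Aim 1.1) counts these consultations by type as well: "LARC consultations (with a scheduled insertion) (overall, and by LARC type [contraceptive implant, IUD".
- Item 7: "relative share of initiations of contraceptive implant and IUD, among LARC initiators".

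Point 3 of Statistical Methods (Aim 1.1) covers items 4 to 7 in one sentence: "bivariate statistical analyses will compare the outcome proportions for contraceptive implant vs. IUD, using Chi-square tests". It gives no table layout, significance level or null share, and no one-sample alternative. The Aim 1.1 methods otherwise consist of frequency tables; no confidence interval is planned.

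**The concern.** A two-group Chi-square needs two sets of units, each with its own denominator, and an outcome that is not the grouping variable. Item 6 meets this: some consultations schedule an implant, others an IUD, and each either leads to insertion or does not.

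Items 4, 5 and 7 do not. Counseling visits (item 4) and method-initiation visits (item 5) do not divide into an implant group and an IUD group; device type is part of the outcome. In item 7 the two shares sum to 1. The two proportions are therefore negatively correlated. A test that treats them as independent uses the denominator twice and takes the variance of their difference to be smaller than it is.

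Comparison by LARC type is a stated part of Aim 1.1, so these p-values are likely to be reported. The three comparisons also reduce to one contrast, implant count against IUD count, whenever the same initiations are counted. Three p-values would then look like three pieces of evidence.

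**Working it through.** **Plan's own figure.** The documents give no error rate, power or sample size for the Aim 1.1 tests, so there is nothing to reproduce. The one power statement belongs to Aim 3.1 and does not bear on this point.

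**Inputs.**
- Expected initiators: n = 102 (Section 4, patient population: "102 LARC insertions (Aim 2").
- Historical split: "129 LARC initiations (86 contraceptive implant, 43 IUD), and 44 LARC initiations (41 implant, 3 IUD" (Power/Sample Size, Aim 3.1).
- Assumed, because not stated: two-sided alpha 0.05, and a null of equal shares.
- Denominators for items 4 and 5: not given, so a range of shares is used.

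**Item 7, asymptotic.** Let p be the implant share.
- Variance of the difference assumed by a two-group test: 2p(1−p)/n.
- True variance, since the difference is 2p̂−1: 4p(1−p)/n.
- The ratio is 2, so the false-positive rate is 2[1−Φ(1.96/√2)] = 16.6%.

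**Item 7, exact at n = 102.** Let d be the difference between the two counts. It must be even.
- The two-group statistic on the table [x, n−x; n−x, x] is 2d²/n. It passes 3.84 from d = 14 (2×196/102 = 3.843).
- The one-sample goodness-of-fit statistic is d²/n. It passes 3.84 from d = 20 (400/102 = 3.92).

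| Test at n = 102, true split 50:50 | False-positive rate |
|---|---|
| Two-group, uncorrected | 19.8% |
| Two-group, Yates | 13.7% |
| Goodness-of-fit | 5.9% |
| Exact binomial | 3.7% |

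**Items 4 and 5.** Let each type be a share p of the one denominator.
- Assumed variance: 2p(1−p)/n. True (multinomial) variance: 2p/n. Ratio: 1/(1−p).
- False-positive rate: 2[1−Φ(1.96√(1−p))].

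| Share of each type | False-positive rate |
|---|---|
| 5% | 5.6% |
| 10% | 6.3% |
| 20% | 8.0% |
| 30% | 10.1% |

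Simulation agrees. With 300 visits and 17% of each type, the two-group test rejected in 7.3% of runs and a one-sample comparison of the counts, (a−b)/√(a+b), in 5.0%. With 1,000 visits and 5.1% of each type, the rates were 5.6% and 5.0%.

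**What it does to a result (item 7).**
- 60 against 42: d = 18. Two-group 2×324/102 = 6.35, p = 0.012. One-sample 324/102 = 3.18, p = 0.075.
- 86 against 43: d = 43. Two-group 2×1849/129 = 28.7. One-sample 1849/129 = 14.3. Both p < 0.001.
- 41 against 3: two-group 65.6, one-sample 32.8. Both p < 0.001.

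**The case against.** The strongest reply is that the plan never says it will treat the shares as independent groups. It says only that Chi-square tests will be used. For one set of initiators, the ordinary Chi-square on a one-way table is a goodness-of-fit test, which is valid for item 7. The two-group version needs an artificial table that enters every initiator twice. This stands in part: the 17% depends on a layout the plan does not fix.

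It does not dispose of the point. One sentence covers items 4 to 7, and for item 6 it must mean a two-group test. The plan uses Chi-square for separate groups everywhere else: patient subgroups in Aim 1.2, implant against IUD initiators in Aim 2.1, and continuation by device in Aim 3.1. Where it wants a one-sample test, as for the primary outcome, it names one and gives the null of 0.753. Even a goodness-of-fit reading lacks its null share. For items 4 and 5, with two proportions over a visible denominator, the two-group layout is the one an analyst would most naturally build.

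Other limits on the point also stand. Aim 1 is secondary and largely descriptive, the historical split is far from 50:50, and 60 against 42 was chosen to fall where the two tests disagree.

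A reader might also infer that reported intervals will be too narrow, or that small monthly comparisons will be distorted. The documents do not support either. No interval is planned for Aim 1.1. Although the measures are to be assessed monthly, the methods attach the month only to the descriptive counts, not to the Chi-square tests.

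**Conclusion.** The point holds as a modest error of specification in a secondary aim. Followed in the sense the plan gives the test elsewhere, the sentence leads to an invalid test for three of the four items it covers.

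For item 7 the false-positive rate would be about 17% asymptotically, and 19.8% uncorrected or 13.7% with Yates at n = 102. These figures assume the two-group layout, two-sided 0.05 and a 50:50 null. They must not be carried over to items 4 and 5, where the rate is about 5.6% to 10% for shares of 5% to 30% each and depends on denominators the documents do not give.

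It would be wrong to infer that the expected finding is in doubt. At a split like 86 to 43 either test shows a clear difference. The error matters only if the two types turn out much closer. The primary continuation analysis is untouched.

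**What to change.** Replace point 3 of Statistical Methods (Aim 1.1) with a statement for each item:

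- **Item 7:** report the implant share among LARC initiators with an exact binomial 95% confidence interval. If a test is wanted, use a one-sample binomial or goodness-of-fit test and state the null share and significance level.
- **Items 4 and 5:** report the proportions by type descriptively. Alternatively, use a one-sample comparison of the two counts, which allows for the shared denominator and holds about 5%. Note that this is the same contrast as item 7 when the same initiations are counted, so it should not be presented as further evidence.
- **Item 6:** keep the two-group Chi-square, or an exact test.

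The cost is a sentence or two in the methods. No new data, visits or change in sample size are needed.
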